### **1.2 Protocol version and amendments**

- Protocol, Final version 1.0, 24 JAN 2017
- Protocol, Amendment 1.0, 12 OCT 2017
- Protocol, Amendment 2.0, 25 OCT 2018
- Protocol, Amendment 3.0, 31 JUL 2020
- eCRF, Final version 1.0, 01MAR 2017
- eCRF, Final version 2.0, 07 JUL 2017

### **1.3 Applicable standards**

- Bayer Health Care: Company Sponsored Non-Interventional Studies (NIS), Global Standard Operating Procedure, SOP ID: BSP-SOP-041, Version 2, 2011
- Bayer Health Care: Development Pharma, Standard Operating Procedure, Observational Studies, SOP ID: BPD-SOP-041, Version 3.0, 07 APR 2014
- GNIS Global Standard Tables, Version 1.0, 17 JAN 2012
- Some of the eCRFs were created new and are non-standard
- Some of the eCRFs are modified standard (started with standard and changed)

## **2 Study objectives**

The study has the following objectives:

- To evaluate the proportion of subjects who experience new onset or worsening chronic lower abdominal and / or pelvic pain who have undergone Essure placement (anyone who has had an attempt at placement defined as an insert that was placed in the operating channel of the hysteroscope will be included in the analysis, regardless of whether or not they are relying on Essure for contraception) compared to the proportion of subjects who had an attempt at laparoscopic tubal sterilization (defined as anyone who has had an incision or puncture of the skin, regardless of whether or not sterilization was successfully completed), and to better characterize these reported outcomes and identify pre-procedural and procedure-related characteristics that may be related to their occurrence.
- To evaluate the proportion of subjects who experience new onset or worsening abnormal uterine bleeding who have undergone Essure placement (as defined above) compared to the proportion of subjects who have undergone laparoscopic tubal sterilization (as defined above)

and to better characterize these reported outcomes and identify pre-procedural and procedure-related characteristics that may be related to their occurrence.

- To evaluate the proportion of subjects who undergo gynecologic or related surgical intervention (including “insert removal” and hysterectomy) after undergoing hysteroscopic sterilization with Essure versus laparoscopic tubal sterilization.
- To identify the proportion of subjects who experience new onset or worsening allergic, hypersensitivity, or autoimmune-like reactions after Essure placement or laparoscopic tubal sterilization and to better characterize these reported outcomes and any characteristics that may be related to their occurrence.
- To collect data on patient reported outcomes in subjects who have undergone hysteroscopic or laparoscopic tubal sterilization procedures.
- To collect rates of adverse events (AEs) in subjects undergoing Essure placement or laparoscopic tubal sterilization

### **3 Study design**

This study is a multicenter, open-label, non-randomized, continuous enrollment, prospective, observational postmarket surveillance study.

Study subjects will be women who are seeking permanent contraception and who have elected to undergo either hysteroscopic sterilization (Essure System ESS305) or laparoscopic tubal sterilization. Candidates who meet the inclusion and exclusion criteria, are willing to participate in the study, and are able to provide informed consent will be eligible for the study.

The sterilization procedure will proceed as it would if the subject were not in the trial. For subjects who elect to have hysteroscopic sterilization, 3 months following the placement procedure, the subject will be scheduled to return to the physician’s office or radiology facility for a confirmation test to evaluate Essure insert location and retention. Upon a satisfactory confirmation test, subject will be instructed to rely on Essure for contraception.

Follow-up contact will take place at 3 months ( $\pm 2$  weeks), 12 months ( $\pm 4$  weeks), 24 months ( $\pm 4$  weeks), 36 months ( $\pm 4$  weeks), 48 months ( $\pm 4$  weeks), and 60 months ( $-4$  weeks,  $+1$  week) post procedure. These visits will collect information that includes (but is not limited to) pelvic / lower abdominal pain, bleeding, gynecological procedures, AEs, and concomitant medication use.

Patient reported outcomes for pain (Patient Reported Outcomes Measurement Information System Scale V1.0, Pain Intensity 3a and Pain Interference 8a Participant Format) will be assessed at Baseline, Week 1, Week 2, Week 3, Week 4, Month 2, Month 3, and then every 3 months starting Month 6 until 36, if the response is “Yes” to the question “Did you experience pain in your pelvic area or in your lower abdomen during the past week?”

Patient reported outcomes for bleeding (Aberdeen Menorrhagia Severity Scale) will be assessed at baseline and then every 3 months starting Month 3 until Month 36.

Patient reported outcomes for health status (Medical Outcomes Study Short Form-36) will be assessed at Baseline, Month 6, Month 12, Month 24, Month 36, and Month 60.

Subjects will also complete a baseline questionnaire (Fibromyalgia Survey Questionnaire) that may help to identify women who are more likely to report pain events.

Subjects will complete Supplemental PRO Questionnaires at 12, 24, 36, 48, and 60 months, and a Social Media Questionnaire at 60 months (or Premature Discontinuation [dropout] visit if applicable).

The final study visit is in the physician's office 60 months (-4 weeks, +1 week) after the procedure.

## **4 General statistical considerations**

All issues concerning subject validity, data consistency checks, as well as coding of medical terms and concomitant medication will be described in detail in the Data Management Plan. All statistical issues including calculated variables are detailed in this Statistical Analysis Plan.

The study is observational and does not allow a randomized decision for treatment allocation. Therefore, the allocation of procedure to a subject is driven by preferences, medical decision, medical circumstances and other information the treating physician requires for the selection of the best option. Allocation bias must therefore be assumed, with consequent potential for confounding. Under such conditions, formal statistical hypotheses of no treatment effect would include an unknown size of bias, as the size of the confounding remains unknown a priori. In particular, the confounding may nullify differences between groups, due to the size of the confounding that cannot be attenuated through analytical methods, but also may inflate differences.

Attempts can be made by analytical procedures to adjust for measured confounding, but still, in this setting, unmeasured confounding cannot be quantified. Several scenarios of analyses are therefore planned to be employed, addressing several of these sources of confounding.

It is expected that, due to the media attention given to the Essure procedure, there will be significant confounding between the 2 treatment groups leading to channeling bias that will be insurmountable with any analytical method.

The analysis must therefore be considered exploratory in nature.

### **4.1 Determination of Sample Size**

Overall enrollment will be dependent on availability of Essure.

Recruitment in the Essure arm is planned to continue as long as Essure is being implanted. Enrollment in the laparoscopic tubal sterilization arm will be ceased once its enrollment reaches approximately 2:1 ratio laparoscopic tubal sterilization : Essure (anticipated).

### **4.2 General principles**

Statistical analyses will be explorative and descriptive in nature and no confirmatory hypothesis tests are intended to be performed; p-values will be interpreted as a metric for uncertainty. Therefore, no adjustment for multiplicity will be necessary.

All endpoints and variables will be analyzed by descriptive statistical methods. The number of data available and missing data, mean, standard deviation, minimum, lower and upper quartiles, median, and maximum will be calculated for continuous data. Frequency tables will be generated for categorical data. They will include the number of missing values as additional categories. Relative frequencies will be shown as percentages which will be calculated as a proportion including the category of missing values. The level of precision is defined in the table and figure shells with place holders for decimal places. Selected continuous variables will be categorized in a clinically meaningful way.

Unless specified otherwise, subjects in the analyses will be presented according to their initial index event.

The main analyses will be performed on the full analysis set as well as on a PS confounder-adjusted population of the full analysis set in order to adjust for measured confounding. Main analyses will also be performed in the full analysis set, adjusted full analysis set, reliance set, and adjusted reliance set. Details for derivation and adjustment are described in Sections 5.1 and 6.5.1.

The statistical evaluation will be performed using the software package SAS release 9.3 or higher (SAS Institute Inc., Cary, North Carolina, USA). Where propensity score design is conducted, SAS, the R package or STATA may be used.

All MedDRA terms or standardized MedDRA queries (SMQs) which are mentioned in this document are taken from the most updated MedDRA version. At the time of the analysis MedDRA concepts may have been changed; in this event, the validity of the terms and SMQs will be re-checked.

### **4.3 Handling of loss to follow-up, premature discontinuation, and censoring**

Subjects who leave the study before reaching the study completion assessment five years after start of the sterilization procedure will be included in the analysis populations, since the analyses are based on all subjects who attempt sterilization.

For subjects who attempt two sterilization methods, or have any hysterectomy (subtotal, total or radical), or have Essure complete removal using a salpingectomy, or device removal not accompanied by sterilization procedure, their data will be censored for analysis purpose on the earliest date of second sterilization method, hysterectomy surgery date, or Essure removal date, for the primary analysis.

Data will be collected for all the subjects until the end of study or early termination.

### **4.4 Handling of missing data**

#### **4.4.1 Date of last contact**

If the subject dies, date of last contact will be the death date. Otherwise, date of last contact will be considered as the maximum of

- Date of end of study;
- Latest AE start date;
- Latest date for follow-up visits.

#### **4.4.2 Study procedure**

##### **Definition of index event and start of observation**

Subjects will be allocated to either hysteroscopic sterilization (Essure) or laparoscopic tubal sterilization by decision of the physician/subject on the basis of baseline characteristics, medical history, preferences, and other criteria. The date of the initial procedure is considered the index date for the study (Day 0).

## **Stop dates**

If the stop dates for AEs are completely missing, the event will be considered to be ongoing at the time of end of study. Completely missing stop dates will not be imputed.

Partially missing stop dates will be set to the latest logically possible date:

- In case that only the day is missing, last day of the month will be imputed;
- In case that the day and the month is missing (i.e., only the year is available) the day and month will be imputed as December 31.
- If the imputed dates are after the date of last contact, it will be set to the date of last contact.

### **4.4.3 Concomitant medication**

For concomitant medication, the following imputation rules will be applied:

#### **Start of concomitant medication**

Partially missing start dates for concomitant medication will be set to the earliest logically possible date:

- In case that only the day is missing, the date will be imputed as the first day of the month.
- In case that the day and the month are missing, i.e. only the year is available the day and month will be imputed as January 1.
- In the cases where the start date is missing completely, it will be replaced with the minimum of January 1 of the year of the initial visit

#### **Stop of concomitant medication**

Partially missing stop dates will be set to the latest logically possible date:

- In case that only the day is missing, it will be imputed as the last day of the month;
- In case that only the day and the month are missing (i.e., only the year is available) it will be imputed as December 31.
- If the imputed dates are after the last date of contact, it will be set to the last date of contact.
- If the stop dates are completely missing, the medication will be considered as ongoing at the time of end of study.

#### **4.4.4 Surgical intervention and other concomitant procedures**

For women who undergo surgical intervention (including “insert removal” and hysterectomy) or other concomitant procedures after undergoing the initial sterilization the following imputation rules will be applied:

##### **Definition of surgical intervention**

Partially missing dates for surgical intervention will be set to the earliest logically possible date:

- In case that only the day is missing, the date will be imputed as the first day of the month.
- In case that the day and the month are missing, i.e. only the year is available the day and month will be imputed by January 1.
- If the imputed surgical date is before the index date, it will set to the index date.

#### **4.4.5 Main outcome events**

Incomplete start dates of outcome events for the time to event analyses will be imputed as follows:

- In case that only the day is missing, the date will be imputed as the first day of the month.
- In case that the day and the month are missing (i.e. only the year is available) the day and month will be imputed as January 1.
- In case the event start date is missing completely, index event date will be used as start date.
- If the imputed start date is before the index date, it will set to the index date.

Incomplete stop dates of outcome events for the time to event analyses will be imputed as follows:

- In case that only the day is missing, it will be imputed with last day of the month;
- In case that the day and the month are missing (i.e., only the year is available) it will be imputed as December 31.
- If the imputed dates are after the last date of contact, it will be set to the last date of contact.
- If the stop dates are completely missing, the event will be considered as ongoing at the time of end of study.

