9.2 Visit description

9.2.1 Screening period

Section modified by Amendment 1 (Section 16.1) and Amendment 2 (Modification 4, Modification 13, Modification 14, Modification 15).

A prospective study subject will receive both written and verbal information about the study, and will have an opportunity to ask questions and should have sufficient time to decide whether or not to participate in the study. The original signed and dated Informed Consent Form (ICF) must be retained in the investigator's study file and a copy must be provided to the subject.

All subjects for whom the ICF is completed successfully will be assigned a subject number.

Subject screening must occur within 6 weeks prior to procedure (Essure placement or tubal ligation).

The following procedures will be conducted during the Screening Visit:

- Signed and dated ICF;
- For the laparoscopic tubal group: receipt of the ACOG patient information brochure and completion of patient checklist for laparoscopic tubal sterilization;
- Demographic data collection including:
 - Smoking history;
 - Alcohol consumption;
 - Previous medication.
- Eligibility criteria;
- Physical examination (performed once, within 6 weeks prior to the procedure)
- Height;
- Weight;
- Vital signs (blood pressure [BP], heart rate [HR]);
- Pelvic examination (an examination performed within the 6 weeks prior to Screening may be used unless the subject history has changed).
- General medical and surgical history, including but not limited to:
 - History of chronic pain conditions;
 - Personal and family history of autoimmune disease;
 - History of allergies / hypersensitivities;
 - Medical or cosmetic implants or piercings, including body tattoos with metallic colorants;
 - Dental history including orthodonture.
- Gynecological medical and surgical history, including but not limited to:
 - Pregnancies;

- Gynecological procedures such as endometrial ablation, oophorectomy, any other relevant gynecological events;
 - Type of contraception used in the past 6 months;
 - Menstrual history;
 - Vaginal bleeding and AUB;
 - Medication use.
- AE assessment;
- Prior and concomitant medications;
- Baseline blood sample collection, as detailed in Section 9.6.3.1, including:
 - Baseline whole blood for the following assays:
 - Human leukocyte antigen (HLA) typing (obtained from lymphocytes);
 - Nickel lymphocyte proliferation test.
 - Baseline serum or plasma:

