9.6.1.3 Assessments and documentation of adverse events

The investigator has to record on the respective CRF pages all AEs occurring in the period between the signing of the informed consent and the end of the follow-up phase; after the end of the follow-up phase there is no requirement to actively collect AEs including deaths. The type of information that should be assessed and recorded by the investigator for each AE is listed in Section [9.6.1.2](#).

“Death” should not be recorded as an AE on the AE page. Instead, “death” is the outcome of underlying AE(s).

For all SAEs, the sponsor has to carry out a separate assessment for expectedness, seriousness, and causal relationship to study procedure.

Investigator responsibility

Investigators must record and document all AEs on the AE CRF.

- If the AE is an SAE or MDR (including device or procedure-related AEs / effects and deaths), it must be reported immediately (within 24 hours) to the relevant institutional review board (IRB) / Ethics Committee (per local requirements) and to the sponsor by the investigator and recorded on the CRF. The investigator will send to the sponsor,

all appropriate paper work (discharge summaries, office notes, etc.) that might be pertinent. Reports relating to the subjects' subsequent medical course must be submitted to the sponsor until the event has subsided or, in case of permanent impairment, until the event stabilizes and the overall clinical outcome has been ascertained.

- If the AE is also a UADE, it must be reported to the sponsor and the reviewing IRB / Ethics Committee (per local requirements) as soon as possible but no longer than 3 working days after becoming aware of the event. The investigator will send to the sponsor all appropriate paperwork (discharge summaries, office notes, etc.) that might be pertinent. Reports related to the subject's subsequent medical course must be submitted to the sponsor until the event has subsided or, in case of permanent impairment, until the event stabilizes and the overall clinical outcome has been ascertained.

Sponsor responsibility

- The Sponsor will be responsible for categorizing SAEs / serious adverse device effect (SADEs) in terms of expectedness, seriousness, and causal relationship to the Essure device when all necessary data are available.

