## 6.4 Outcome endpoints and variables

The main objective of this observational study is to evaluate under routine clinical practice conditions the incidence of important treatment-emergent AEs under hysteroscopic sterilization (Essure) and laparoscopic tubal sterilization. An AE is considered as treatment-emergent when it starts or worsens on or after the index date and up to the date of subject withdrawal or the censoring date, as described in Sections 4.3 and 6.1.3.

The outcome endpoint and variables are presented in Table 2. The descriptive analysis will be performed for all the variables listed below and the comparative analysis will be performed only for the main endpoints.

For the main endpoints, the subject incidence (regardless of the time each subject is “at risk”) is the number of subjects with treatment-emergent events divided by the number of subjects at risk.

Laboratory evaluation results will be compared to their normal ranges. Any values out of normal ranges will be identified. The change from baseline for each laboratory parameter will also be presented for each post-baseline visit.

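### SAP 4.4.5 moves imputed outcome-event start dates up to the index date even when the recorded month or year already proves onset before the procedure

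*SAP*

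**What the plan says.** The rule in SAP 4.4.5 is introduced with "Incomplete start dates of outcome events for the time to event analyses will be imputed as follows". Its steps are:

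- Day missing: "In case that only the day is missing, the date will be imputed as the first day of the month".
- Day and month missing: "the day and month will be imputed as January 1".
- Nothing recorded: "In case the event start date is missing completely, index event date will be used as start date".
- Floor: "If the imputed start date is before the index date, it will set to the index date".

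The index date is the date of the initial procedure, Day 0 (SAP 4.4.2). SAP 6.4 states: "An AE is considered as treatment-emergent when it starts or worsens on or after the index date". Day 0 is a reporting interval of its own for the main endpoints (SAP 6.4.1). For a woman with an event, time at risk runs from index to the first event (SAP 6.4.2).

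The investigator must record "all AEs occurring in the period between the signing of the informed consent and the end of the follow-up phase" (Protocol 9.6.1.3). Consent is taken at the Screening Visit, and "Subject screening must occur within 6 weeks prior to procedure" (Protocol 9.2.1). Under Protocol 9.6.1.1, a condition that begins or deteriorates after consent is an AE, while one present before consent and unchanged in intensity is medical history.

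**The concern.** The AE data can contain pain and bleeding that began or worsened between consent and sterilization. If such an event is fully dated, it stays before index. If only its month or year is recorded, the floor carries it to Day 0, even when that month or year ended before the procedure. The less precise record turns a non-outcome into an outcome.

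The study objectives concern new or worsening pain and bleeding after sterilization. An event that the record itself places before the procedure would be charged to the procedure, enter the Kaplan-Meier and Cox analyses at time zero, and add an event with no person-time to the exposure-adjusted incidence. If the imputed date also drives the treatment-emergent flag, the event would appear in the Day 0 incidence row as well.

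**Working it through.** The plan gives no figure to reproduce here. The check is a literal application of the rule, followed by an illustration of how often a partial date settles the question.

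**1. The rule applied.** For an incomplete date, final start = max(imputed start, index date); a complete date is left alone. The event is treatment-emergent if final start ≥ index. Take an index date of 10 April 2018:

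| Recorded start | Imputed | Final start | Status | What the record shows |
|---|---|---|---|---|
| MAR 2018 | 1 March | 10 April, Day 0 | treatment-emergent | onset before index is certain |
| 25 MAR 2018 | none needed | 25 March, Day −16 | not treatment-emergent | onset before index is certain |
| APR 2018 | 1 April | 10 April, Day 0 | treatment-emergent | ambiguous |
| 2018 | 1 January | 10 April, Day 0 | treatment-emergent | ambiguous |
| missing | index | 10 April, Day 0 | treatment-emergent | ambiguous |

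Only the first row is wrong. The first two rows could describe the same event and get opposite results. A year-only date meets the same problem when the index date falls early in a year and the AE is recorded with the previous year.

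**2. Share of pre-procedure AEs whose partial date proves pre-index onset.** Assumptions: index dates spread evenly over a 365-day year, and onset uniform over the W days before index. W = 42 is the 6-week screening limit; 28 and 14 represent shorter intervals between consent and procedure.

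*Day missing.* With index on day d of its month, onset L days earlier falls in an earlier month when L ≥ d. Each index date contributes max(W − d + 1, 0) such cases out of W.

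- W = 14: the sum over d = 1 to 14 is 105 per month; 12 × 105 = 1,260; 1,260 / (365 × 14) = 1,260 / 5,110 = 0.247.
- W = 28: the sum over d = 1 to 28 is 406 per month; 12 × 406 = 4,872; 4,872 / (365 × 28) = 4,872 / 10,220 = 0.477.
- W = 42: a 31-day month gives 31 × 43 − 496 = 837, a 30-day month 30 × 43 − 465 = 825, a 28-day month 28 × 43 − 406 = 798. The total is 7 × 837 + 4 × 825 + 798 = 9,957; 9,957 / (365 × 42) = 9,957 / 15,330 = 0.650.

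*Day and month missing.* The same count by day of the year gives [W(W + 1)/2] / (365 W) = (W + 1)/730, which is 15/730 = 0.021, 29/730 = 0.040 and 43/730 = 0.059 for W = 14, 28 and 42.

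**3. What else could catch these events.** The sensitivity analysis in SAP 6.8 lifts the censoring rules and leaves start dates as imputed. Protocol 10.3 excludes pain and bleeding AEs with another apparent cause, but it is not a date rule. Chronic pain requires a duration of more than 182 days, or pain ongoing at end of study with a start 182 days before (SAP 6.4). A shifted pain AE must meet this counted from index. Bleeding has no duration requirement.

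**The case against.** The strongest reply is about scope. SAP 4.4.5 is worded for the time-to-event analyses, and Table 2 describes the pain and bleeding endpoints as AEs after the sterilization procedure. One can read the section as dating events that have already qualified as post-procedure, so that the floor merely stops a true outcome from drifting before Day 0. The parallel floor in SAP 4.4.4 works that way, because that section is confined to surgery after the initial sterilization. The reading is possible, but 4.4.5 carries no such limit and no passage sets the treatment-emergent flag before imputation. What stands is that use of the imputed date for the flag and the Day 0 incidence row is inferred from the absence of another rule.

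The second reply is rarity. AEs are assessed at screening and again at the procedure visit, and the data capture system runs completeness checks (Protocol 12.1), so few pre-procedure AEs may lack a full date. This stands as a limit on size.

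Four stronger readings are tempting, and the documents do not support them:

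- That every pre-procedure AE becomes a Day 0 outcome. Complete dates are untouched. Saying that all day-missing pre-procedure AEs reach Day 0 only restates the rule, and it includes same-month cases where the floor is a reasonable convention.
- That such AEs are bound to occur because women with pelvic pain or menorrhagia are eligible. A pre-consent condition at unchanged intensity is medical history. Only onset or deterioration between consent and procedure is exposed.
- That 65% is the expected share. It assumes the full 42 days, which is a maximum.
- That using the index date for a completely missing start is also an error. That convention is conservative and contradicts nothing recorded. An onset placed after the last symptom-free contact would be another debatable choice.

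**Conclusion.** The concern holds in a narrow form. As written, the floor overrides a recorded month or year that rules out onset on or after index. In the time-to-event analyses this follows directly from 4.4.5; in the incidence tables it follows by inference.

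The documents do not say how many AEs are affected, so no effect on any endpoint can be stated, nor its direction in the comparison of the two groups. The shares above are conditional on an AE arising before the procedure and being incompletely dated, and they rest on assumed uniform onset. They describe how often a partial date would prove pre-index onset, not how many events will be misplaced. Bleeding is the more exposed endpoint because pain must also pass the 182-day requirement. The correction is worthwhile because the misclassification is avoidable and almost free to remove.

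**What to change.** Amend SAP 4.4.5 as follows:

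1. Apply the index-date floor only when the known part of the start date is compatible with a start on or after index.
2. If the known month or year lies wholly before that of the index date, keep the AE as pre-index and not treatment-emergent, unless worsening on or after index is recorded.
3. State that the same rule governs the treatment-emergent flag in 6.4.
4. Report how many outcome events have a start date floored to index, and how many have a start date that is completely missing.

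Keep the existing rule for completely missing start dates. The cost is a few lines of SAP text and code; no new data are needed.
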